4.2 Study Design

The study is a multicenter, randomized, double-blind, and placebo-controlled Phase 1b SAD and MAD design. The subject, investigator, and site personnel (except pharmacist) will be blinded to treatment, while the sponsor will be unblinded. Sponsor personnel will be unblinded to subject

treatments in order to permit real-time interpretation of the safety, pharmacokinetic, and pharmacodynamic data. The site monitor will remain blinded to individual subject treatment allocation until all monitoring of study data has been completed. To minimize the potential for bias, individual subject treatment randomization information will not be released to the investigator or blinded study site personnel until the study database has been locked.

Eligible subjects with homozygous $\Delta F508$ CF will be randomized at a 3:1 ratio to receive either QR-010 or placebo via oral inhalation (nebulization). This study will be conducted in North America and select European countries.

[figure not shown]
The study includes 2 stages. The first stage is a single ascending dose-escalation (SAD) design to determine safety and tolerability of a single dose of QR-010. The second stage is a multiple ascending dose escalation (MAD) design to further assess the safety, tolerability, and exploratory efficacy of 12 doses of QR-010 over 4 weeks. All doses will be administered in a clinical setting.

For the SAD cohorts, subjects will receive the dose in an inpatient observation unit and be observed for a total 4 days, and will be discharged on Day 4. Subjects will return for PK and safety follow-up as an outpatient on Day 8 (End of Study Visit).

For the MAD cohorts, subjects will receive doses 1 through 12 in a clinic while under observation. On Day 1 and Day 3 subjects will be observed until 12 hours post dose. Following the last dose (dose 12), subjects will return twice for PK sampling, and will be evaluated 7 and 28 days after the last visit for this additional safety monitoring and sampling for PK.

A schematic of the study design is presented in Figure 3.

Figure 3: PQ-010-001 Study Schematic

Single Ascending Dose Escalation Cohorts: The first two subjects of each cohort may be dosed on the same day, at least 4 hours apart. If no significant AEs occur, the remainder of the cohort may be dosed at least 24 hours later, with at least 1 hour between subjects.

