The AEs of Interest listed in Table 2 are AEs commonly seen with inhaled products. If AEs of interest occur at a Grade 2 level or higher in a single subject in a cohort, then an additional 4 subjects will be added to the cohort. Any of the Grade ≥ 2 toxicities shown in Table 2, as well as

any other respiratory AEs reported, will be evaluated and considered when making dose escalation decisions. If no additional subjects experience any Grade ≥ 2 AEs of Interest, dose escalation may proceed (if recommended by the DSMC).

The Investigator will base decisions to de-escalate to a lower dose, hold the dose (delay or skip), or discontinue study drug for an individual subject using the CTCAE (modified for CF) toxicity grades, in consultation and agreement with the Sponsor’s Medical Monitor. In addition to the CTCAE (modified for CF) toxicity grades, the Investigator should also review the stopping rules in Section 5.5.3 with regard to decreases in FEV₁.

For the multiple dose cohorts, subjects who experience a DLT (defined in Section 4.4) should be discontinued from study drug (whether or not the event resolves), and the End of Treatment Visit procedures should be conducted. An End of Study Visit should also be conducted 28 days after the last study drug dose.

Table 2: Adverse Events of Interest

| Adverse Event of Interest | Symptoms (Grade ≥ 2 per CTCAE or as Specified Below) |
|--------------------------------------|------------------------------------------------------------------------------------------------------------------------------------------|
| Atelectasis | Symptomatic (eg, dyspnea, cough); medical intervention indicated (eg, chest physiotherapy, suctioning); bronchoscopic suctioning |
| Hypotension | non-urgent medical intervention indicated |
| Bronchospasm | symptomatic, medical intervention indicated |
| Liver Function Test Elevation | alanine aminotransferase (ALT) > 3-5 x ULN or aspartate aminotransferase (AST) > 3-5 x ULN AND a doubling from the baseline value |
| Pneumonitis | Symptomatic; medical intervention indicated; limiting instrumental ADL |
| Crackles | Scattered or focal |
| Dyspnoea | Shortness of breath with minimal exertion; limiting instrumental ADL |
| Hypoxia | Decreased oxygen saturation with exercise (eg, pulse oximeter < 88%); intermittent supplemental oxygen |

ADL = Activities of Daily Living

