12.3.2 Assessment of the Relationship of Adverse Events to Study Drug

The Investigator will make a causality assessment about the relationship of each AE to study drug. Treatment-related conditions must be distinguished from disease-related conditions. To ensure consistency of AE and SAE causality assessments, Investigators should apply the following general guideline:

Not Related: The AE has an etiology other than the study drug (eg, preexisting medical condition, underlying disease, intercurrent illness, or concomitant medication); and/or the AE has no plausible temporal relationship to administration of the study drug (eg, cancer diagnosed 2 days after first dose of study drug).

Related: There is a plausible (possible, probable, or definite) temporal relationship between the onset of the AE and administration of the investigational product, and the AE cannot be readily explained by the subject's clinical state, intercurrent illness, or concomitant therapies; and/or the AE follows a known pattern of response to the investigational product; and/or the AE abates or resolves upon discontinuation of the investigational product or dose reduction and, if applicable, reappears upon rechallenge.

Note: The Investigator's assessment of causality for individual AE reports is part of the study documentation process and will be recorded in the subject's medical record, AE CRF, and SAE form if applicable. AEs recorded without the Investigator's assessment of the relationship to study drug will be followed up until causality is assigned.

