13.7 Safety Analyses

13.7.1 Treatment Emergent Adverse Events

A treatment emergent AE (TEAE) is defined as an event that was not present prior to administration of the first dose of study drug and present after the first dose or if it represents the exacerbation of an event that was present prior to the first dose.

AEs noted during the study will be coded to system organ classes (SOCs) and preferred terms (PTs) using the MedDRA dictionary. The overall incidence of TEAEs will be summarized by dose group and classified by SOC and PT. Deaths, AE severity, seriousness, relationship to study drug and study discontinuation due to AE will also be tabulated by dose group. An AE will be considered drug-related if the Investigator indicated the event is at least “possibly” related or if the relationship is missing. AEs with missing start dates, but with stop dates overlapping into the treatment period will be counted as treatment emergent. All AEs will be listed in subject listing, and summarized by numbers and percents of subjects by dose for each portion of the study separately. If a subject reports the occurrence of a particular event more than once, the most severe of those events will be included in the summary tables of TEAEs, and the most severe of the treatment-related events will be included in the summary tables of treatment-related events.

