### 2.5.2. Unblinding

The DSMC is unblinded to the Study Treatment. Safety data from each cohort will be provided unblinded and evaluated by the DSMC at the end of each cohort, prior to escalation to the next dosing level. Additionally if AEs of interest occur at a Grade 2 level or higher, as defined in the protocol, they will be provided to the DSMC for evaluation in a timely fashion (i.e., without waiting for completion of the cohort) to support dose escalation decisions and determination of dose limiting toxicity events.

Sponsor personnel may be unblinded to subject treatments in order to permit interpretation of the safety, pharmacokinetic, and pharmacodynamic data. The site monitor will remain blinded to individual subject treatment allocation until all monitoring of study data has been completed. To minimize the potential for bias, individual subject treatment randomization information will not be released to the investigator or blinded study site personnel until the study database has been locked.

In the event of a medical emergency, when knowledge of treatment assignment is needed for immediate medical management of the subject's health, Investigators can obtain unblinded treatment assignment through the centralized IWRS system at any time. Thorough documentation of the rationale for unblinding is required. Consultation of the study Medical Monitor is recommended for all unblinding requests.

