#### 4.10.1. Adverse Events

##### 4.10.1.1. General Adverse Event Reporting

Adverse events will be summarized with MedDRA System Organ Class (SOC) and Preferred Term, by subject incidence rates, therefore, in any tabulation, a subject contributes only once to the count for a given adverse event (SOC or preferred term or AESI).

A treatment emergent Adverse Event (TEAE) is defined as an event with start date at/or after first dose.

An overall summary of TEAEs will include the number of

- Subjects with at least one TEAE,
- Number of TEAE,
- Subjects with study drug-related TEAEs,
- Subjects with device-related TEAEs,
- Subjects with TEAEs by maximum severity grade,
- Subjects with serious AEs,
- Subjects with TEAEs Leading to Treatment Discontinuation,
- Subjects with TEAEs Leading to Study Discontinuation,
- Deaths

The overall incidence of TEAEs will be summarized by treatment group and classified by SOC and PT. Reporting will include reports for Serious AEs, AEs leading to treatment discontinuation, deaths, AEs related to study drug, AEs related to device. AEs by SOC and PT will be presented by maximum severity.

An AE will be considered drug-related if the Investigator or Sponsor indicated that the event is coded "possibly" or "definitely" related to study drug or if the relationship is missing. The same definition applies for relationship to device.

AE intensity is graded on a 5 level category (Mild/Grade 1, Moderate/Grade 2, Severe/Grade 3, Life threatening/Grade 4, Death/Grade 5). Maximum intensity per PT is reported.

TEAEs will be listed in subject listings. Listings of Serious TEAEs, Death, Grade 2 or higher TEAEs will also be presented.

A listing for the non-treatment emergent events (with start date and time prior to first dose) will be provided, the listing will be provided only if events are collected.

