#### 4.10.1.2.8. AESI8: Hypoxia

Hypoxia is defined as: Pulse Oximeter < 88%

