## **5. CHANGES TO PLANNED ANALYSES**

As of this date, there have been no changes between the protocol-defined statistical analyses and pharmacokinetics analyses those presented in this statistical plan.

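### Two SAP safety rules differ from the protocol: relatedness adds Sponsor judgement to an Investigator-only rule, and the hypoxia AESI rests on an oximeter reading alone

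*SAP*

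**What the plan says.** **Relatedness.** Protocol 13.7.1 states: "An AE will be considered drug-related if the Investigator indicated the event is at least" possibly related, or if the relationship is missing. Protocol 12.3 and 12.3.2 place causality with the Investigator: "The Investigator will make a causality assessment about the relationship of each AE to study drug". SAP 4.10.1.1 states: "An AE will be considered drug-related if the Investigator or Sponsor indicated that the event is coded" possibly or definitely related, again with missing counted as related.

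**Blinding.** Protocol 4.2 blinds the subject, investigator and site personnel other than the pharmacist, "while the sponsor will be unblinded". SAP 2.5.2 is softer: "Sponsor personnel may be unblinded to subject treatments in order to permit interpretation of the safety" and the PK and PD data.

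**Hypoxia.** Protocol Table 2 (section 4.3), in a column for Grade 2 or higher events, describes hypoxia as "Decreased oxygen saturation with exercise (eg, pulse oximeter < 88%); intermittent supplemental oxygen". SAP 4.10.1.2.8 has only "Hypoxia is defined as: Pulse Oximeter < 88" per cent. Protocol 8.4 takes oximetry at rest, seated. SAP 4.10.1.2 tabulates AESIs by SOC and PT, with a separate summary for AESI4 alone.

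**Declared changes.** SAP section 5 says: "As of this date, there have been no changes between the protocol-defined statistical analyses" and those in the SAP. The later SAP for post hoc analyses deals with efficacy endpoints and alters neither safety rule.

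**The concern.** The related-AE tables are a main way of separating drug effect from background CF morbidity. Under protocol 13.7.1 they rest on the judgement of a blinded assessor. The SAP lets a second party's judgement turn an event into a related one, and that party may know the allocation. No text keeps the Sponsor's causality assessor blinded. A reader who trusts SAP section 5 would take the tables to be those the protocol defined.

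For hypoxia, the final AESI table may not match the events handled during the study. SAP 2.5.2 sends AEs of interest to the DSMC on the protocol's definition, and under protocol 4.3 one Grade 2 or higher AE of interest adds 4 subjects to the cohort. A cohort could therefore be expanded for a hypoxia event that the AESI8 row does not show.

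**Working it through.** The plan gives no figure to reproduce, and the sample size has no power basis. The check is a comparison of rules, with one calculation for scale.

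**1. Relatedness rule.** Write I for an Investigator call of related, S for a Sponsor call of related, and M for missing.

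- Protocol 13.7.1: related = I or M.
- SAP 4.10.1.1: related = I or S or M.
- Difference, with the categories held the same: S and not I and not M. This set is empty or positive, so the Sponsor route can only add events.

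**2. Categories.** The protocol's threshold is at least *possibly*, and the Related category in 12.3.2 covers possible, probable and definite. The SAP names only *possibly* and *definitely*. If the CRF has a *probable* level, which cannot be seen from the documents, the SAP as worded would not count it. The net change from restoring the protocol rule could therefore go either way. The SAP also does not say whether missing means either assessment or both.

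**3. Scale.** Inputs: 6 QR-010 and 2 placebo subjects per planned cohort, 4 cohorts in each part (protocol 13.2 and 4.3), and one placebo column per part (SAP Tables 3 and 4).

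- One reclassified QR-010 subject: 1/6 = 16.7 percentage points.
- Placebo per part: 4 × 2 = 8; one reclassified subject: 1/8 = 12.5 percentage points.

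**4. AESI8 against Table 2.** The SAP wording can be read in two ways: (a) any reading below 88%, or (b) a hypoxia AE accompanied by a reading below 88%.

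| Case | Table 2 description | AESI8, reading (a) | AESI8, reading (b) |
|---|---|---|---|
| Reported Grade ≥2 hypoxia AE, no reading <88% | Covered | Not counted | Not counted |
| Hypoxia AE treated with intermittent oxygen, no reading <88% | Covered | Not counted | Not counted |
| Resting reading <88%, no AE reported | Not as described | Counted | Not counted |

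The first two rows fail on either reading. The third depends on (a), which is the plain one. However, a bare reading has no SOC or PT and so has no place in the table planned in SAP 4.10.1.2. The direction of the net error is unknown.

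**5. What does not use these rules.** Overall TEAE incidence by SOC and PT and the Grade 2 or higher listing (SAP 4.10.1.1); pulse oximetry summaries and listings (SAP 4.10.3); DLTs, which the DSMC adjudicates (protocol 13.7.2, SAP 4.10.1.3); and the MTD, which is set from DLTs (protocol 4.5).

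**The case against.** The best defence on relatedness is that an either-assessor rule is inclusive. Protocol 13.1 says that in this first-in-human trial every AE counts towards the safety profile unless it is plainly unrelated, and the SAP rule leans the same way. That weakens any claim of harm. It does not make the rule the one in 13.7.1, nor does it make SAP section 5 correct.

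A reader might infer that an unblinded sponsor biased the related-AE comparison. The documents do not support this. They do not say that the person judging causality for the Sponsor knew the allocation, and they hold nothing on how Sponsor calls would fall by arm.

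On hypoxia, Table 2 serves cohort expansion and escalation, and protocol 13.7 plans no AESI table. The AESI output is thus an SAP addition, and AESI8 does not contradict a protocol-defined analysis in the way the relatedness rule does. That stands. The defect is that a table borrowing Table 2's label leaves out events Table 2 describes.

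A reader might also infer that frequent resting oximetry would inflate AESI8. SAP 4.10.1.1 counts each subject once per AESI, and subjects with resting saturation below 92% at screening are excluded, so the number of readings is no measure of error. Nor is information lost: hypoxia AEs remain in the TEAE tables, and low saturations remain in the oximetry outputs.

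**Conclusion.** Both differences are in the current text. The relatedness rule is an undeclared departure from protocol 13.7.1, and the no-change statement in SAP section 5 is wrong for it. AESI8 is incomplete against Table 2 on either reading, and its wording is unclear about readings without an AE.

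Severity is minor. Relatedness affects the related-TEAE row of the overall summary and the related-AE table by SOC and PT; AESI8 affects one AESI category. A single subject is worth 16.7 points in a planned QR-010 group and 12.5 points in a planned placebo column; these figures assume cohorts of planned size with no expansion. The documents give no event rates, so the number of misclassified events cannot be estimated. A reader might go on to infer that escalation or the MTD is compromised. It is not, because those decisions rest on DSMC review and adjudicated DLTs, not on these derivations.

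**What to change.** **Relatedness.** Use the protocol 13.7.1 rule for the main related-AE outputs: Investigator judgement of at least possibly related, which takes in any probable category, or missing. Show Sponsor attribution in a separate display. State how missing is defined, and declare any remaining departure in SAP section 5.

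**AESI8.** Reconcile the rule with Table 2. Add a branch for reported Grade 2 or higher hypoxia AEs, including those treated with oxygen, and show readings below 88% with no AE as a separate line. This concerns what the table counts; it takes no position on which clinical definition of hypoxia is right.

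**Cost.** SAP wording and light programming. AE grade, treatment and relationship are recorded under protocol 8.1, and oximetry is already scheduled, so no new collection is needed. Counts may move in either direction: related events may fall when Sponsor-only calls are taken out or rise if a probable category is restored, and AESI8 may gain reported AEs while reading-only cases move to their own line.

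### The SAP's list of codes for a drug-related AE omits *probable* and *Related*, which the protocol's threshold includes, and declares no change; the effect is confined to the related-AE summaries and depends on the eCRF code list

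*SAP*

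**What the plan says.** Three passages bear on when an adverse event is counted as related.

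- **Protocol 12.3.2** gives investigators two categories. The negative one begins "Not Related: The AE has an etiology other than the study drug". The positive one, *Related*, begins "There is a plausible (possible, probable, or definite) temporal relationship between the onset of the AE and administration of the investigational product" and adds further conditions. The judgement is entered in the "medical record, AE CRF, and SAE form if applicable". Events without an assessment are to be chased until one is assigned.
- **Protocol 13.7.1** gives the analysis rule: "An AE will be considered drug-related if the Investigator indicated the event is at least “possibly” related or if the relationship is missing". This is a threshold, so every level at or above *possibly* is in.
- **SAP 4.10.1.1** gives its own analysis rule. It opens "An AE will be considered drug-related if the Investigator or Sponsor indicated that the event is coded" and goes on to name the codes: "coded 'possibly' or 'definitely' related to study drug or if the relationship is missing". This is a closed list of two terms plus missing. It then adds: "The same definition applies for relationship to device".

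SAP section 5 states that nothing has changed between the protocol-defined analyses and the SAP. SAP 1.1 refers to the eCRF of 17 March 2017, but neither document reproduces its causality codes.

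**The concern.** A threshold and a closed list agree only if the list names every level at or above the threshold. This list does not: *probable* is missing, and so is *Related*, the only positive category that Protocol 12.3.2 defines. Taken literally, the SAP counts an event that nobody assessed as drug-related and leaves out one judged probably related. Neither document gives a reason for that ordering. It also sits badly with Protocol 13.1, which says that in this first-in-human trial all events inform the safety profile unless clearly unrelated.

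At stake are the lines for drug-related and device-related events in the overall TEAE summary, and the separate related-event tables by dose group. Dose groups are small, so the classification of a single subject shows. A reader of the study report would also take SAP section 5 at its word and assume that the protocol's rule had been used.

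**Working it through.** The plan gives no figure to reproduce. The check is to take each causality level that appears in the documents and classify it under the two analysis rules for study drug.

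| Level | Protocol 13.7.1 | SAP 4.10.1.1 as written |
|---|---|---|
| Not Related | not counted | not counted |
| Possible | counted | counted |
| Probable | counted | **not counted** |
| Definite | counted | counted |
| Related (no grade) | counted in substance | **not counted** |
| Missing | counted | counted |

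The entry for plain *Related* under the protocol is an inference: 13.7.1 does not name that category, but its definition in 12.3.2 starts at possible, so it meets the threshold. The two rules differ on exactly two of the six levels, and in both the SAP is the narrower.

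For the device, neither 12.3.2 nor 13.7.1 gives a rule, so there is no protocol text to contradict. The gap there is only that the SAP carries over a list that omits *probable* and *Related*.

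What this means in practice depends on the unseen eCRF:

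1. Positive codes are only possibly and definitely: no event is lost, and the SAP list is the protocol threshold spelled out.
2. Positive codes are possibly, probably and definitely: events coded probably are not counted.
3. A two-level field, Not Related or Related: no assessed event matches the list, and only missing ones count.

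Cases 2 and 3 are upper limits, because the SAP accepts a code from the Investigator or the Sponsor. An event that the Investigator called probable still counts if the Sponsor coded it possibly or definitely.

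Scale for one subject, from the planned numbers in Protocol 13.2 and SAP 4.1 (6 active and 2 placebo per cohort, four cohorts in each part):

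- Active dose group: 1/6 = 16.7 percentage points.
- Placebo column, pooled within SAD or MAD as in SAP Tables 3 and 4: 2 × 4 = 8 subjects, 1/8 = 12.5 percentage points.

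A subject leaves a given row only if no other event in that row still counts, since the SAP tabulates by subject. These fractions show what one misclassified subject would do. They do not estimate how many there would be.

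**The case against.** The best defence is that the SAP speaks of how the event is coded and puts two terms in quotation marks, which reads like eCRF code names. It also covers device-relatedness, for which Protocol 12.3.2 has no scale, so its wording may come from the eCRF rather than from the protocol. If so, no event is misclassified and section 5 is right about the category list. This cannot be ruled out, and it limits the point. It does not remove it: an eCRF with only those two positive codes would itself depart from Protocol 12.3.2, and the SAP would still owe the reader the mapping.

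Three stronger readings are tempting, and the documents support none of them.

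- *Events judged probable or Related do fall out, perhaps every related event.* This needs an eCRF that holds those codes, which is not shown. Total loss needs a two-level field, yet Protocol 13.7.1 speaks of *possibly*, which presupposes grades. A table in which only missing values counted as related would probably be noticed in programming.
- *The primary safety result is affected.* The primary endpoints in Protocol 4.1.1 are AE incidence and severity and the occurrence of DLTs, none restricted by causality. All TEAEs are still tabulated by SOC, PT and maximum severity and are listed. The DLT definition does not use relatedness, and the DSMC adjudicates DLTs. The individual stopping rules in Protocol 5.5.3.2 turn on suspected relationship during the trial, not on this derivation.
- *The tables are biased in favour of QR-010.* Against the protocol rule, any loss can only lower the related counts. But the rule applies to placebo as well, so the direction of any effect on the comparison with placebo is not established.

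**Conclusion.** The SAP rule is wrong as written: it is narrower than Protocol 13.7.1 on two levels, has no place for the positive category in Protocol 12.3.2, and is not declared in SAP section 5. This rests on the text alone.

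The number of events affected rests on the eCRF code list, which is not available, and on Sponsor coding. It ranges from none to all events coded *probable* or *Related*. The consequence is confined to the drug-related and device-related summaries. Severity is low.

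**What to change.** Replace the rule in SAP 4.10.1.1 with: *An AE is drug-related (device-related) if the relationship is at least possibly related (possible, probable, definite, or Related) or is missing.* Add a short mapping from each eCRF causality code to counted or not counted, for drug and for device.

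A rule that counts everything other than *Not Related* looks simpler but should not be used. If the eCRF has a level below possibly, such as unlikely, that rule would count it and so contradict Protocol 13.7.1.

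The cost is one SAP sentence, the mapping, and one line of derivation code. No data change. If the only positive eCRF codes are possibly and definitely, the results stay the same. With the threshold restored, SAP section 5 needs no entry for the category list.
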